3 OBJECTIVES AND ENDPOINTS

No visual rehabilitation procedures are currently existing for children with visual field loss consecutive to brain tumor. The visual and auditory modalities of the 3D-MOT IVR stimulation program could potentially improve visual perception in the peripheral fields and saccades/volitional eye movements towards pre-designated targets. Improved oculomotor control will also result in better fixation stability which in turn ameliorates visual perception (reading, visual field).

PRIMARY OBJECTIVE:

Feasibility:

- Adherence to the home-based stimulation protocol. Each time the patients performed an audiovisual IVR session, data about the session (device ID#, subject #, date/time, time to complete the task/block, number of tasks/blocks performed, total stimulation time, total duration of the session) are recorded by the NeurofyResearch application in the Oculus Go and sent through Wi-Fi to a dedicated and secured laboratory computer.
- VRISE questionnaire scores recorded before and after each session and sent through Wi-Fi to a dedicated and secured laboratory computer in real-time.
- Retention rate.

SECONDARY OBJECTIVE:

Secondary endpoint measures will be performed at Toronto Western hospital during baseline and final visit (visit 1 and 6) and at 1 month (visit 7) and 6 months (visit 8) follow-up.

Visual acuity:

- Best Corrected Visual Acuity (BCVA) scores for distance and near vision – ETDRS/Colenbrander charts.
- Fixation stability - MAIA microperimeter, CentreVue

- Contrast sensitivity – FACT test.

Field of Vision:

- Humphrey full field 120 – Humphrey Field Analyzer 3, Zeiss
- Esterman binocular field - Humphrey Field Analyzer 3, Zeiss

Reading Speed:

- Minnesota Low Vision Reading - MNREAD test.

Quality of life:

- Children’s Vision Function Questionnaire (39 questions)

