Primary outcome corresponds to the feasibility of the study in terms of adherence, retention rates and recruitment. We specified, a priori, 4 feasibility objectives for our pilot study to be considered successful:

1. $\geq 8/10$ patient (80%) completed the protocol.
2. IVR stimulation protocol is considered complete if the patient performed ≥ 12 sessions out of 15.
3. ≤ 3 consecutive VRISE score < 25 per patient during the treatment period.
4. ≤ 2 dropouts (20%) for cybersickness (discomfort symptoms experienced in VR)

Completion of the sessions will be monitored in real-time. After each block, a data sheet (.csv, 2 kb) containing device ID#, subject #, date/time, time to complete the task/block, number of tasks/blocks performed, total stimulation time, total duration of the session will be sent though Wi-Fi to a dedicated and secured laboratory computer in real-time (if no Wi-Fi access is available at the end of each block, data are stored in the device and sent as soon as Wi-Fi is again available – data storage capacity 500 Mo. No extra costs are incurred to the patients' Wi-Fi plan for sending data). Each session contains 3 data sheets. A session is considered complete when 3 blocks of 5 min stimulation are performed. If no data sheets are received on the lab's computer for a period of 3 consecutive days or missed/incomplete sessions are observed, the participant's parent will be contacted by phone and email to identify the cause (no Wi-Fi, Oculus Go malfunction, dropout) and appropriate action will be taken. Before and after each session, the participant will answer to the VRISE questionnaire (5 questions scored 1 to 7 using the Oculus Go). After the completion of the questionnaire, the detailed score will be sent though Wi-Fi to a dedicated and secured laboratory computer in real-time.

Secondary outcome corresponds to potential effectiveness of IVR stimulation measured by visual perception and quality of life assessed following standard procedures used in low-vision rehabilitation²⁷ and collected at the low-vision clinic by ophthalmologists. Endpoints will measure change from baseline at 2 and 4 weeks in:

- Best Corrected Visual Acuity, distance and near vision (ETDRS chart, Colenbrander chart).
- Mean fixation stability (MAIA micro-perimeter).
- Contrast sensitivity (FACT test).
- Points not seen – Humphrey full field 120 (HFA3, Zeiss)
- Points not seen – Esterman binocular field (HFA3, Zeiss)

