4.3 END OF STUDY DEFINITION

A participant is considered to have completed the study if he or she has completed all phases of the study including the last visit or the last scheduled procedure shown in **Section 1.3, Schedule of Activities (SoA)**. The duration of participation for each individual participant who completes all study visits will be 7 months.

The end of the study is defined as completion of the last visit or procedure shown in the SoA in the trial globally. It is estimated that it will take 24 months from when the study opens to enrollment until the end of the study.

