7 DISCONTINUATION AND WITHDRAWAL

Discontinuation from visual training does not mean discontinuation from the study, and remaining study procedures should be completed as indicated by the study protocol. If a clinically significant finding is identified (including, but not limited to changes from baseline) after enrollment, the PI or qualified designee will determine if any change in participant management is needed. Any new clinically relevant finding will be reported as an Adverse Event (AE).

Withdrawn patient will go for a final visit at the clinic with primary and secondary outcome assessment. Primary outcomes (adherence, VRISE scores, retention) collected until the withdrawal date will be analyzed. Secondary outcomes (BCVA, fixation stability, contrast sensitivity, reading speed, visual fields and quality of life) will be assessed during final visit and analyzed.

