8 STUDY ASSESSMENTS AND PROCEDURES

A participant will be considered lost to follow-up if they fail to return for two scheduled visits and is unable to be contacted by the study site staff.

The following actions must be taken if a participant fails to return to the clinic for a required study visit:

- The site will attempt to contact the participant and reschedule the missed visit within 24 hours and counsel the participant on the importance of maintaining the assigned visit schedule and ascertain if the participant wishes to and/or should continue in the study.
- Before a participant is deemed lost to follow-up, the Principal Investigator or designee will make every effort to regain contact with the participant (where possible, 3 telephone calls and, if necessary, a certified letter to the participant's last known mailing address or local equivalent methods). These contact attempts should be documented in the participant's medical record or study file.
- Should the participant continue to be unreachable, they will be considered to have withdrawn from the study with a primary reason of lost to follow-up.

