9 STATISTICAL CONSIDERATIONS

9.1 STATISTICAL HYPOTHESES

- Primary Endpoint(s):

Feasibility is considered when the following primary endpoints criteria are met:

1. $\geq 8/10$ patient (80%) completed the protocol.
2. IVR stimulation protocol is considered complete if the patient performed ≥ 12 sessions out of 15.
3. ≤ 3 consecutive VRISE score < 25 per patient during the treatment period.
4. ≤ 2 dropouts (20%) for cybersickness (discomfort symptoms experienced in VR)

- Secondary Endpoint(s):

Secondary endpoint measures will be performed at Toronto Western hospital during baseline (visit 1), after 2 weeks (visit 2), after treatment at 4 weeks (visit 3) and at 1-month (visit 4) and 6 months (visit 5) follow-up. Results will be compared to baseline.

Visual acuity:

- Best Corrected Visual Acuity (BCVA) scores for distance and near vision – ETDRS/Colenbrander charts.
- Fixation stability - MAIA microperimeter, CentreVue
- Contrast sensitivity – FACT test.

Field of Vision:

- Humphrey full field 120 – Humphrey Field Analyzer 3, Zeiss
- Esterman binocular field - Humphrey Field Analyzer 3, Zeiss

Reading Speed:

- Minnesota Low Vision Reading - MNREAD test.

Quality of life:

- Children's Vision Function Questionnaire (39 questions)

- Exploratory Endpoint(s):

None

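### Retention is a named primary outcome, but no success criterion tests all-cause retention after session 12

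*Combined protocol and SAP*

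**What the plan says.** Retention is named as a primary outcome in several places. Section 3 lists "Retention rate" under the primary objective, with no time point, denominator or threshold. Section 4.1 states: "Primary outcome corresponds to the feasibility of the study in terms of adherence, retention rates and recruitment"; section 9.4 repeats this. Section 7 adds: "Primary outcomes (adherence, VRISE scores, retention) collected until the withdrawal date will be analyzed".

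Sections 4.1, 9.1 and 9.4 then give the same four criteria for success:

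1. At least 8 of 10: "patient (80%) completed the protocol".
2. The stimulation protocol counts as complete with at least 12 of the 15 sessions.
3. A limit on runs of low VRISE scores per child during treatment.
4. "≤ 2 dropouts (20%) for cybersickness (discomfort symptoms experienced in VR".

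Study completion is a separate notion. Under section 4.3 a child completes the study "if he or she has completed all phases of the study including the last visit", and section 7 says that stopping the training is not the same as leaving the study. No criterion uses the section 4.3 definition.

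On denominators, section 9.2 plans 10 children, section 7.2 replaces withdrawn children until 10 are evaluable, and section 9.3 defines the intention-to-treat population as everyone registered.

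**The concern.** A success rule should be able to fail when the outcome it is meant to judge fails. Here the verdict covers adherence, retention and recruitment, but the criteria cover home sessions, VRISE scores and one cause of dropout. Criterion 2 can be met from the headset's session records alone, without attendance at any visit after baseline.

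The secondary outcomes are compared with baseline at 2 weeks, 4 weeks, 1 month and 6 months, so visits 3 to 5 carry most of the information on potential effectiveness. Followed as written, the rule could report the pilot as feasible in terms of retention when few or no families returned for those visits.

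**Working it through.** **Inputs.** Ten children (9.2); at least 8 completers, at least 12 of 15 sessions, at most 2 cybersickness dropouts (9.1); session and visit days (1.3); replacement to 10 evaluable (7.2); intention-to-treat as all registered (9.3).

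**The plan's percentages.** 8/10 = 80% and 2/10 = 20%. Both reproduce, and both imply a denominator of 10. No sample size or power calculation is given, so there is none to reproduce.

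**What the criteria limit, with a fixed 10 and no replacements.** A child who leaves before session 12, for any reason, is a non-completer. At least 8 completers leaves at most 10 − 8 = 2 non-completers, so criterion 1 caps all-cause dropout before session 12 at 2 of 10. It also caps cybersickness dropout in that period at 2. Splitting 10 children into completers, early cybersickness dropouts, early dropouts for other reasons and children who stay but do too few sessions gives 10 splits that meet criterion 1; 0 of them break criterion 4. On this reading criterion 4 can change the verdict only through cybersickness dropout after session 12, for example 10 completers of whom 3 then leave for that reason.

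**What they leave open.** The schedule marks 15 home session days: 1, 3, 5, 7, 9, 11, 13, 14, 15, 17, 19, 21, 23, 25, 27. The twelfth is day 21 if none is missed. The last visit is on day 200, so 200 − 21 = 179 days follow in which loss for reasons other than cybersickness affects no criterion. If 10 children do 12 sessions with acceptable VRISE scores and none returns for visits 3 to 5, then criterion 1 is met (10/10), criterion 4 is met (0 dropouts for cybersickness) and 6-month retention is 0/10.

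**Effect of replacement.** Suppose 3 children leave before session 12 and are replaced: 13 registered, 10 evaluable, and 8 to 10 of the evaluable children complete.

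| Reason for the 3 early dropouts | Criterion 1 on 10 evaluable | Criterion 1 on all 13 registered | Criterion 4 |
|---|---|---|---|
| Cybersickness | met (80% to 100%) | not met (at best 10/13 = 76.9%) | not met (3 > 2) |
| Any other reason | met (80% to 100%) | not met (at best 10/13 = 76.9%) | met (0) |

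On 10 evaluable children, criterion 4 is not implied by criterion 1. However, the second row passes, and it would also pass with 5 replaced (10/15 = 66.7% of those registered, at best). The plan does not say which denominator applies.

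**How an 8-of-10 retention rule would behave.** With independent children and true retention p, P(at least 8 of 10) = 45p⁸(1 − p)² + 10p⁹(1 − p) + p¹⁰. The plan gives no expected retention, so these values of p are assumptions:

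| Assumed p | P(at least 8 of 10) |
|---|---|
| 0.6 | 0.167 |
| 0.7 | 0.383 |
| 0.8 | 0.678 |
| 0.9 | 0.930 |

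Under the present rule, loss after session 12 for reasons other than cybersickness leaves the verdict unchanged at every p.

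**The case against.** The best defence is that the synopsis gives the primary endpoint as completion of the home procedure, that the 1- and 6-month visits serve secondary outcomes, and that retention is to be analysed even without a threshold. On that view, making 6-month attendance a condition of success is a preference. The documents also describe no follow-on trial that would depend on it. This would carry weight if the success verdict were confined to home completion. It is not: section 4.1 names retention as part of what the criteria judge.

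Several stronger readings are tempting, and the documents do not support them:

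- A reader might infer that dropout for reasons other than cybersickness affects no criterion at all. Before session 12 it counts against criterion 1, at least when 10 children are counted without replacements.
- A reader might infer that criterion 4 is always redundant before session 12. That needs a fixed 10; with replacement and 10 evaluable children it can fail on its own.
- The lost-to-follow-up rule (sections 7.3/8) applies "if they fail to return for two scheduled visits" and the child cannot be contacted. A reader might infer that a child who misses only visit 5 is never counted as lost. The same text also treats a child who misses a required visit and stays unreachable as withdrawn and lost to follow-up.
- A reader might infer that recruitment is wholly untested. At least 8 completers requires at least 8 recruited; what goes untested is the pace, or stopping at 8 or 9.

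**Conclusion.** The point holds for all-cause retention after session 12 and for attendance at visits 3 to 5. The four criteria can all be met with anything from 0/10 to 10/10 children seen at 6 months, provided later losses are not for cybersickness. This follows from the wording of the criteria and needs no assumed rate; the day-21 figure assumes no missed session.

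Loss up to session 12 is limited to 2 of 10 only if replacements are not counted. If criterion 1 is scored on 10 evaluable children, early dropout for reasons other than cybersickness has no limit either. If it is scored on everyone registered, early loss is limited but later loss still is not. On every reading the gap after session 12 remains. It should be closed because it affects the stated success decision, not only the reporting.

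**What to change.** Leave criterion 4 unchanged, so that the tolerability limit is not weakened, and add a separate criterion in sections 4.1, 9.1 and 9.4 using the plan's own 80% threshold:

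*At least 8 of the first 10 registered children (80%) attend visit 3 (4 weeks) and visit 5 (6 months). Leaving the study for any reason counts as not retained, and replacements do not count.*

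State that criterion 1 is scored on the same first 10 registered children, and report retention for all registered children alongside. Scoring by attendance means that the verdict does not depend on how the lost-to-follow-up text is read.

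For recruitment, report the time taken to register 10 children against the timeline in section 4.3 ("It is estimated that it will take 24 months from when the study opens to enrollment" until the end of the study). With 7 months of participation, the last child would have to be registered by month 24 − 7 = 17. A pass/fail limit there would leave no time for replacements, so reporting is enough.

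The cost is one added criterion and a sentence on the denominator; attendance and registration are already recorded. Success becomes somewhat harder to declare: if true retention were 80% (assumed), the new criterion alone would be met with probability 0.68, and at 90% with probability 0.93.

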9.2 SAMPLE SIZE DETERMINATION

The CONSORT guidelines state that sample size calculations may not be required for feasibility studies, however it is important that the sample be representative of the target study population³³. For this pilot study, we will recruit 10 patients.

9.3 POPULATIONS FOR ANALYSES

The following study populations are defined and will be analyzed as specified below. The population evaluable for safety will be the safety population.

The Intent to Treat (ITT) population: the total population of patients registered in the study.

Safety population: all registered participants who received at least one visual training session.

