1.2 SCHEMA

1.3 SCHEDULE OF ACTIVITIES (SOA)

	Inclusion	Baseline	Treatment																Follow-up	
Day	0	0	1	3	5	7	9	11	13	14	15	17	19	21	23	25	27	28	58	200
Visit #		1								2								3	4	5
Fixation stability		X								X								X	X	X
BCVA		X								X								X	X	X
Contrast sensitivity		X								X								X	X	X
MNREAD test		X								X								X	X	X
CVFQ		X								X								X	X	X
Humphrey Full Field 120		X																X	X	X
Esterman binocular		X																X	X	X
VRIFE	X		X	X	X	X	X	X	X	X	X	X	X	X	X	X	X			
IVR	X		X	X	X	X	X	X	X	X	X	X	X	X	X	X	X			

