2.3 RISK/BENEFIT ASSESSMENT

Potential Risks:

There are no risks for patients enrolled in the study. The use of IVR may cause moderate dizziness, nausea or disorientation for continuous stimulation above 10 minutes²⁵. If nausea, dizziness or disorientation is experienced during IVR stimulation, stopping the VR stimulation immediately restores normal condition²⁵. A recent study on the effects of IVR in 4-10 years old children indicate great tolerability with a prevalence of discomfort and induced effect of IVR lower than reported in adults²⁴.

Patients will be assessed for IVR sensitivity using the Virtual-Reality Induced Symptoms and Effects (VRISE) questionnaire score at inclusion²⁶ (exclusion criteria: three (3) consecutive VRISE score < 25).

At-home VR stimulation will be 5 minutes of continuous stimulation as specified in the “Study Intervention” section, below the critical 10 minutes threshold inducing effects and symptoms^{25,26}.

There are no risks for the community/public nor for the institution.

Potential Benefits:

We anticipate the HH patients will be able to adhere and comply to the home-based audiovisual stimulation program without any symptoms or effects.

We expect the potential benefits IVR stimulation will correspond to:

- an improved fixation stability,
- an enhanced reading speed.
- an improved field of vision

All together increasing self-dependency and quality of life which ultimately impact health care cost by:

- reducing the burden of disease,
- decrease of the global cost of vision impairment.

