5.2 EXCLUSION CRITERIA

An individual who meets any of the following criteria will be excluded from participation in this study:

1. Ocular diseases
2. Both eyes with media opacity that impairs microperimetry testing.
3. Inability to perform during testing and training.
4. Consumption of psychoactive drugs.
5. 3 consecutive VRIFE scores < 25 at inclusion.
6. History of vertigo or dizziness
7. Prior vision rehabilitation interventions.

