5.4 SCREEN FAILURES

Screen failures are defined as participants who consent to participate in the clinical trial but are not subsequently randomly assigned to the study intervention or entered in the study. A minimal set of screen failure information is required to ensure transparent reporting of screen failure participants. Minimal information includes demography, screen failure details and eligibility criteria.

Individuals who do not meet the criteria for participation in this trial (screen failure) because of a inability to follow the visual and auditory stimuli and training instructions may be rescreened after 4 weeks to a maximum of 3 times. Rescreened participants should be assigned the same participant number as for the initial screening.

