6 STUDY INTERVENTION

6.1 STUDY INTERVENTION(S) ADMINISTRATION

6.1.1 STUDY INTERVENTION DESCRIPTION

The device used is the commercially available virtual-reality, standalone, head mounted display Oculus Quest 2 (Facebook Technologies, Qualcomm, Xiaomi). There are currently 34 clinical trials registered on Clinicaltrials.gov using the Oculus Go or Quest: 12 in the US and 4 in Canada. [name] lab (co-

investigator) is currently running a clinical study using the Oculus Quest 2 in elderly patient with macular degeneration (NCT04685824, UHN REB approval 20-6143). The application uploaded in this device is the NeurofyResearch application, developed and owned jointly by UHN and Neuropowertrain (Research and Collaboration Agreement). It is a modified version of the Neurofy application, owned by Neuropowertrain, used for perceptual/cognitive training in professional athletes.

[figure not shown]

Figure 2: representation of the 3D-MOT stimulation procedure:

1. 8 spheres appear in the headset **2.** One sphere is cued (red) and returns to yellow after 5 seconds. **3.** All spheres start moving randomly for 20 seconds. **4.** After 20 seconds, the spheres stop moving. **5.** The patient must select using laser pointer (white) the ball corresponding to the cued one. **6.** The result is displayed corresponding to either a hit (correct selection) or a miss (wrong selection). Sequence returns to 1. for the next trial.

Audiovisual IVR stimulation procedure

This procedure corresponds to:

- 1 session every 2 days (± 1 day) for 4 weeks.
- 1 session = 3 blocks of 15 audiovisual stimulation tasks (2 min break between each block).
- 1 task = 20 seconds audiovisual IVR stimulation (3D-MOT + correlated sound).

The audiovisual stimulation task (the *NeurofyResearch* application) involves the 3D multiple-object-tracking (3D-MOT) paradigm composed of 8 high-contrast spheres which features are adapted to the visual ability of low-vision patients (luminosity = 100cd/m², size = 1.57° of visual angle). The spheres move for 20 seconds following random linear paths, bouncing on one another and on the walls of a virtual 3D cube when collisions occur. The overall span of the movement of the spheres covers 80° and 60° of horizontal and vertical visual angle respectively. The initial speed of the spheres is adjustable, from 3°/s. to 240°/s. and determined during the inclusion visit (figure 2).

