8.2.4 TIME PERIOD AND FREQUENCY FOR EVENT ASSESSMENT AND FOLLOW-UP

All Adverse Events (AEs) or Serious Adverse Events (SAEs) due to IVR stimulation resolve as soon as the stimulation stops²⁵. Investigators will follow-up the participant at 24 hours by phone or email assessing the severity of the AEs using the VRISE questionnaire

AE reporting will begin at the time of signing of the informed consent (screening) and will continue until discharge from the study. AEs will be elicited by:

- spontaneous report by participants and/or parents,
- by 3 consecutive VRISE scores < 25,
- by observation (by the investigators and/or healthcare staff).

AEs will be documented in the source documents and the eCRF within 24 hrs.

All AEs and SAEs occurring while on study must be documented regardless of relationship. Information to be collected includes event description, date and time (if possible) of onset, date and time (if possible) of resolution/stabilization of the event, outcome, and the assessment of seriousness, expectedness, relationship to study intervention and severity by a delegated qualified physician.

Any baseline condition recorded in the medical history that deteriorates at any time during the study, will be recorded as an AE or SAE.

Changes in the severity of an AE will be documented to allow an assessment of the duration of the event at each level of severity to be performed.

Events will be followed for outcome information until resolution or in the opinion of the PI or qualified physician delegate, the participant is stable and does not require further follow-up, or the participant is deemed lost to follow-up.

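### The safety population leaves out children exposed to VR at inclusion and screened out for symptoms, so the planned AE rates describe only children who passed that screen

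*Combined protocol and SAP*

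**What the plan says.** **Analysis sets.** Section 9.3 of the combined protocol and SAP has two sets. The ITT set is everyone registered. The other reads "Safety population: all registered participants who received at least one visual training session", and the section adds: "The population evaluable for safety will be the safety population". Neither *registered* nor *visual training session* is defined.

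**Exposure at inclusion.** The schedule of activities (section 1.3) marks both the IVR row and the questionnaire row in the inclusion column. Section 2.3 says: "Patients will be assessed for IVR sensitivity using the Virtual-Reality Induced Symptoms and Effects (VRISE) questionnaire score at inclusion". Section 6.1.1 has the starting sphere speed set at the same visit.

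**Exclusion on the result.** Section 5.2 excludes a child with "3 consecutive VRIFE scores < 25 at inclusion". I read VRIFE there as VRISE, because section 2.3 gives the same rule under that name.

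**What counts as an AE, and from when.** The AE definition in section 8.2 treats a VRISE score under 25 as an adverse event. Section 8.2.4 says: "AE reporting will begin at the time of signing of the informed consent (screening) and will continue until discharge from the study".

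**Screen failures.** Section 5.4 covers children who consent but do not enter the study. For them, "Minimal information includes demography, screen failure details and eligibility criteria".

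**Planned safety output.** The opening of section 8.2 plans rates of AEs. Section 9.4.4 plans descriptive summaries of average VRISE scores.

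**The concern.** The screening visit does two things at once: it gives the exposure whose safety is being studied, and it removes children according to their reaction to it. Their low scores are adverse events under the protocol's definition and fall inside its AE collection period. Yet the only set evaluable for safety begins at the first training session of a registered participant. The AE collection window and the safety denominator do not match, and the children lost in between are lost because of the safety outcome.

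At stake is how the AE rates and VRISE summaries are read. A reader planning a larger study wants to know how often children with hemianopia react badly to this headset. The tables as defined answer that only for children who got past the screen.

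**Working it through.** **Step 1. Is the inclusion exposure a training session?** As the table reads, the IVR row in section 1.3 carries 16 marks: 1 at inclusion and 15 in the treatment columns (days 1 to 27). Sections 4.1 and 6.1.2 give 15 sessions in total. So 16 − 1 = 15, and the stated total is met without the inclusion exposure. Section 6.2.1 also describes visual training as something done at home with the headset provided. Both points say that the inclusion exposure is not a training session.

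**Step 2. Is a child who fails the screen registered?** Section 5.4 describes a screen failure as someone who consented but was not entered in the study. On the plain reading such a child is not registered, and so is in neither the ITT nor the safety set.

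**Step 3. Does the child have an AE?** Each score below 25 is an AE, and collection starts at consent. A child excluded under section 5.2 has three such scores. The events are recorded, but no set contains them.

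**Step 4. Direction.** Let *d* be the children with an AE among 10 enrolled (section 9.2) and *s* the children exposed at inclusion and screened out for low scores.

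- Rate in the safety set: *d*/10.
- Rate among all exposed: (*d* + *s*)/(10 + *s*).
- The second exceeds the first when 10(*d* + *s*) > *d*(10 + *s*), that is, when *s*(10 − *d*) > 0. This holds whenever *s* ≥ 1 and *d* < 10.

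This assumes that all 10 enrolled children start training and that no exposed child is screened out for another reason. If *u* event-free children were exposed and then screened out for other reasons, the condition becomes *s*(10 − *d*) > *d* × *u*. With *d* = 0 it still holds for any *s* ≥ 1, although the all-exposed rate would be lower than shown below.

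**Step 5. Size.** The documents give no screen-failure count, so *s* is assumed over a range. Take *d* = 0 and *u* = 0. The exact (Clopper–Pearson) 95% limits for *x* of *n* are the 0.025 quantile of Beta(*x*, *n* − *x* + 1) and the 0.975 quantile of Beta(*x* + 1, *n* − *x*). For *x* = 0 the lower limit is 0 and the upper limit is 1 − 0.025^(1/*n*), which for *n* = 10 is 0.308.

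| Screened out for low scores (assumed) | Safety set as defined | All exposed | Exact 95% CI, all exposed |
|---|---|---|---|
| 0 | 0/10 = 0% | 0/10 = 0% | 0–31% |
| 1 | 0/10 = 0% | 1/11 = 9% | 0.2–41% |
| 2 | 0/10 = 0% | 2/12 = 17% | 2–48% |
| 3 | 0/10 = 0% | 3/13 = 23% | 5–54% |
| 5 | 0/10 = 0% | 5/15 = 33% | 12–62% |

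The plan has no figure of its own for the AE rate to reproduce.

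**The case against.** Five counter-arguments deserve weight.

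- **The conventional set.** A safety set of participants who received the intervention is usual practice, and the VRISE screen is a declared eligibility rule. For children who pass it, the rate in the safety set is the right one. This stands. The limit is on what the rate describes.
- **Nothing is hidden.** Section 5.4 keeps screen-failure details and section 8.2.4 requires AEs to be documented from consent. This also stands: the gap is in the analysis set and denominator, not in the records. It does not supply a rate, because no planned table combines those events with an exposed denominator.
- **Undefined terms.** If consent counted as registration and the inclusion exposure as a session, these children would be in. Sections 5.4 and 6.2.1 and the count of 15 sessions point the other way. If the broader meaning is intended, the text must say so.
- **Different exposures.** The length of the inclusion exposure is not stated, so pooling it with a 15-session home programme mixes unlike things. This is fair, and it is why the two periods should be shown separately.
- **The cybersickness criterion.** A reader might infer that the feasibility limit of at most 2 dropouts for cybersickness is also biased downward. The documents do not support that. It is a primary criterion analysed by ITT and it counts dropouts; a child who never entered cannot drop out. Redefining the safety set would not move it. The criterion on consecutive low scores is likewise confined to the treatment period.

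**Conclusion.** The point holds as a mismatch between AE collection and the safety set. On the plain reading of section 9.3, AEs at inclusion in children excluded for those same AEs fall outside every analysis set. The AE rates of section 8.2 and the VRISE summaries of section 9.4.4 then describe only children who passed the screen, and understate the rate among all exposed children.

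With no events in 10 enrolled children, the all-exposed rate runs from 0% if none is screened out for low scores to 33% (12–62%) if five are. These counts are assumptions; if no child is screened out for symptoms, nothing changes.

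Two stronger readings fail. The enrolled-only rate is not wrong for enrolled children. Nor did they all tolerate the screen without symptoms: exclusion needs three low scores in a row, so a child with one or two can still enter.

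**What to change.** In section 9.3:

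- Define *registered* and *visual training session*.
- Define the safety population as every consented child with at least one IVR exposure, including the one at inclusion. Alternatively, keep the present set and add a second, all-VR-exposed set.
- In sections 8.2 and 9.4.4, report AEs and VRISE scores at inclusion separately from those during home training.
- State the number of children exposed at inclusion and the number excluded there for VRISE scores, next to the tolerability results.
- Leave the ITT set, the feasibility thresholds and the eligibility rule as they are.

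The cost is wording. The inclusion scores are already scheduled and AEs are already collected from consent. The downside is that the AE rate may look less favourable, and a single pooled figure would mix two kinds of exposure unless the periods are shown apart.
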